This amended protocol (Amendment 09) is considered to be substantial based on the criteria set forth in Article 10(a) of Directive 2001/20/Ethics Committee (EC) of the European Parliament and the Council of the European Union.

OVERALL RATIONALE FOR THE AMENDMENT

The overall rationale for this amendment is as follows:

- To include the recommendations that were developed for the COVID-19 pandemic period and were shared with the sites/Investigators. These recommendations will remain applicable after the end of the pandemic, especially the information regarding the post-infusion surveillance period.
- To revise the text in Sections 12, 13, and 14 as per the current Sanofi protocol template to use the updated wordings that are compliant with general guidance, including monitoring techniques.
- To update Section 8.1 for details regarding home infusions to harmonize this text across the different studies included in the avalglucosidase alfa development program.

Protocol amendment summary of changes table

Section Number and Name	Description of Change	Brief Rationale
Protocol Amendment Summary of Changes Table	Document formatting revision.	To update document history and provide overall rationale for the amendment.
Section 8.1 Investigational medicinal product	Requirement for patients to remain in the hospital or in the infusion center for the observation period related to onset of AEs was revised from 2 hours to 1 hour and the following text was added: "In case the patient does not stay for this observation period (eg, as part of contingency measures for a regional or national emergency that is declared by a governmental agency), the Investigator (or appropriate designee) will contact the patient to ensure that no AEs occurred during the observation period."	Due to COVID-19 pandemic restrictions, the observation period after the infusions were performed at the study site or infusion center was shortened or skipped for patient's safety reasons. Also to lighten this period after the end of the pandemic and in order to obtain information in case this observation period is not performed, the observation time after the end of infusion is reduced to 1 hour.
Section 8.1 Investigational medicinal product	Under "Home infusion" subsection, the text was updated to harmonize with other studies included in the avalglucosidase alfa development program.	The home infusion text is amended to allow patients to benefit from home infusion sooner in case of an unexpected event (ie, after 6 months free of IARs instead of 12 months) or to resume home infusion sooner after interruption for IAR during home infusion. Some text is also updated to harmonize across the other studies included in the avalglucosidase alfa development program.
Section 10.4.3 Instructions for reporting serious adverse events	Text was deleted regarding proactively sending the SAE-related reporting documents via fax or as photocopy.	As per recent Sanofi procedures, the direct sending of source documents to the Sponsor (except to Pharmacovigilance department) is no more recommended.
Section 12 Regulatory, ethical, and study oversight considerations; Section 13 Study monitoring; Section 14 Additional requirements	Headings, subsections, and corresponding text were fully updated in Sections 12, 13, and 14 to reflect current practices as outlined in the current protocol template, including monitoring techniques.	To align with current protocol template.
Section 17.2 Appendix 2: Protocol amendment history	Added new Section 17.2.8.	To incorporate the changes from amended protocol 07 to amended protocol 08.
Throughout	Typos have been corrected where necessary. Minor editorial and document formatting revisions are made.	To provide clarifications.

NAMES AND ADDRESSES OF

COORDINATING INVESTIGATOR

Name:
Address:

Tel:
Fax:
E-mail:

MONITORING TEAM'S REPRESENTATIVE

Name:
Address:

Tel:
Fax:
E-mail:

SPONSOR

Company:
Address:

Genzyme Corporation
[name]
[name]
USA

OTHER EMERGENCY TELEPHONE NUMBERS

CLINICAL TRIAL SUMMARY

COMPOUND: GZ402666 - avalglucosidase alfa (neoGAA, GZ402666)	STUDY No.: LTS13769
TITLE	An open-label, multicenter, multinational extension study of the long-term safety and pharmacokinetics of repeated biweekly infusions of avalglucosidase alfa (neoGAA, GZ402666) in patients with Pompe disease.
INVESTIGATOR/TRIAL LOCATION	Sites that have previously participated, or that are currently participating, in an avalglucosidase alfa study.
STUDY OBJECTIVES	Primary objective: To assess the long-term safety and pharmacokinetics (PK) of avalglucosidase alfa in patients with Pompe disease who have previously completed an avalglucosidase alfa study. Secondary objective: To assess the long-term effect of avalglucosidase alfa on pharmacodynamic and exploratory efficacy variables to assess if the benefits of avalglucosidase alfa are maintained and to assess the time course of response.
STUDY DESIGN	Open-label, multicenter, multinational extension study of the long-term safety and PK of repeated biweekly infusions of avalglucosidase alfa in patients with Pompe disease.
STUDY POPULATION Main selection criteria	Inclusion criteria: I 01. Patients with Pompe disease who previously completed an avalglucosidase alfa study. I 02. The patient and/or their parent/legal guardian is willing and able to provide signed informed consent, and the patient, if <18 years of age, is willing to provide assent if deemed able to do so. I 03. The patient (and patient's legal guardian if patient is <18 years of age) must have the ability to comply with the clinical protocol. I 04. The patient, if female and of childbearing potential, must have a negative pregnancy test [urine beta-human chorionic gonadotropin (B-hCG)] at baseline. Note: Sexually active female patients of childbearing potential and male patients are required to practice true abstinence in line with their preferred and usual lifestyle or to use two acceptable effective methods of contraception, a barrier method such as a condom or occlusive cap (diaphragm or cervical/vault cap) with spermicidal foam/gel/film/cream/suppository and an established non-barrier method such as oral, injected, or implanted hormonal methods, an intrauterine device, or intrauterine system for the entire duration of the treatment period.

	
Exclusion criteria:
 
E 01. The patient is concurrently participating in another clinical study using investigational treatment.
 
E 02. The patient, in the opinion of the Investigator, is unable to adhere to the requirements of the study.
 
E 03. The patient has clinically significant organic disease (with the exception of symptoms relating to Pompe disease), including clinically significant cardiovascular, hepatic, pulmonary, neurologic, or renal disease, or other medical condition, serious intercurrent illness, or extenuating circumstance that, in the opinion of the Investigator, precludes participation in the study or potentially decreases survival.

Total expected number of patients	This is an ongoing extension study, and therefore, the number of patients will be determined by enrollment from other avalglucosidase alfa studies.
Expected number of sites	The number of sites will be determined by enrollment of patients from other avalglucosidase alfa studies.
STUDY TREATMENT	
Investigational product	Avalglucosidase alfa (recombinant human α -glucosidase conjugated with synthetic bis-mannose-6-phosphate-Man6 glycan).
Formulation and route of administration	Sterile lyophilized powder administered by intravenous (IV) infusion following reconstitution and dilution.
Dose regimen	20 mg/kg of body weight every other week (qow).
PRIMARY ENDPOINT	
Primary endpoint:
 
Safety:
 
Assessment of adverse events (AEs)/treatment-emergent AEs (TEAEs), including infusion-associated reactions (IARs) and deaths.
 
Physical examination.
 
Clinical laboratory evaluations including hematology, biochemistry, and urinalysis.
 
Vital signs.
 
Body weight.
 
12-lead electrocardiogram (ECG).
 
Immunogenicity assessments.

SECONDARY AND EXPLORATORY ENDPOINTS	
Secondary endpoints:
 
Pharmacokinetics
 
Estimates for C_{max}, AUC_{last}, AUC, $t_{1/2z}$, CL, and Vd.
 
Pharmacodynamics
 
Skeletal muscle magnetic resonance imaging (MRI).
 
Skeletal muscle needle or open biopsy.
 
Urinary Hex4.
 
Exploratory plasma and urine biomarkers.
 
Pharmacogenetics
 
Serum skeletal muscle ribonucleic acid (RNA) expression analysis.
 
Plasma circulating microRNA analyses.

	
Exploratory Endpoints:
 
Efficacy
 
6-minute walk test (6MWT).
 
Pulmonary function testing (PFT) endpoints.

ASSESSMENT SCHEDULE	
Refer to study and period flow charts.
 
Medical/surgical history, and Pompe disease history, including GAA gene mutations, will be imported from the patient's prior avalglucosidase alfa study file in the database when possible.

STATISTICAL CONSIDERATIONS	
Out of range laboratory values, vital signs, and ECGs will be flagged by the Investigator as clinically significant or non-clinically significant abnormalities. The clinically significant abnormalities will be recorded as AEs and included in the TEAE counts.
 
Treatment-emergent adverse events will be tabulated (counts and percentages).
 
Infusion-associated reactions and discontinuations due to AEs will be summarized.
 
Descriptive statistics will be generated by dose level and time points for selected parameters of interest.
 
In addition, raw data and changes from baseline for selected parameters will be summarized by descriptive statistics and/or plots.
 
Descriptive statistics for actual values and changes from baseline will be generated by time point for selected safety parameters of interest. Data may also be plotted. For the purpose of analysis, baseline will be prior to the first dose of GZ402666 in any prior avalglucosidase alfa study.
 
Pharmacokinetics
 
Pharmacokinetic parameters will be summarized for each dose level and study visit by means of descriptive statistics.
 
Pharmacodynamics
 
Changes over time in tissue glycogen content in the lower extremity muscle will be summarized using descriptive statistics. Evaluation of intact muscle and fatty replacement from MRI will be descriptive using a grading scale and, if feasible, quantitative using a numeric method of determining the degree (%) of overall fatty replacement of muscle from the skeletal muscle MRI and an individual (%) measure for the quadriceps. A correlative measure comparing the biopsied muscle and its MRI counterpart will also be performed. Relationship between pharmacodynamic and efficacy endpoints will be explored using graphic display or correlational analysis as appropriate.
 
Exploratory efficacy
 
Observed measurements and changes from baseline will be provided for each endpoint: 6MWT and PFT parameters.

DURATION OF STUDY (per patient)	
The duration of the study for each patient is initially 6 years. Each patient will continue with the study until the patient withdraws, the Investigator withdraws the patient, or the Sponsor terminates the study.
 
An additional follow-up phase will begin after the patient has completed the 6-year study period, and will last until avalglucosidase alfa is approved in the patient's country, except in the UK, Germany and

	Denmark, where the duration of the additional follow-up phase will be up to the approval in the country or limited to a maximum of 2 years, whichever occurs first (ie, for patients in the UK, Germany and Denmark, the total study duration per patient is 8 years at the maximum including the initial 6-year period and the additional 2-year follow-up).
STUDY COMMITTEES	Steering Committee: No Data Monitoring Committee: Yes Adjudication Committee: No

1 FLOW CHARTS

1.1 GRAPHICAL STUDY DESIGN

Baseline^a 
• Informed consent• Inclusion/exclusion criteria• Urine pregnancy test (females only)• ECG• Demographics• Medical/surgical history• Pompe disease history, including GAA mutation• ECG, hematology, biochemistry and urinalysis data prior to first avalglucosidase alfa infusion• Results of MRI baseline from previous avalglucosidase alfa study to be obtained	Biweekly^b 
• Infusion of avalglucosidase alfa• Vital signs	Monthly 
• Urine pregnancy test (females only)• For first 3 years since enrollment: Biochemistry• For first 6 months: Anti-avalglucosidase alfa antibodies and neutralizing antibodies in ADA-positive patients	Quarterly 
• Body weight• After first 6 months: Anti-avalglucosidase alfa antibodies and neutralizing antibodies in ADA-positive patients• After first 3 years since enrollment: Biochemistry	Every 6 Months 
• Physical examination• ECG• Hematology and urinalysis• Anti-avalglucosidase alfa IgG antibodies (only patients who were previously treated with alglucosidase alfa)• 6MWT• PFT	At 6 Months, Yearly Thereafter 
• avalglucosidase alfa plasma samples for PK analysis• Urine Hex4 sample collection• Exploratory biomarker urine sample collection• Exploratory biomarker plasma sample collection• microRNA plasma sample collection	Every 2 Years 
• MRI• Skeletal muscle needle or open biopsy^c• Serum samples for skeletal muscle RNA expression analysis^c
--	--	---	---	--	---	--

Every Visit: Adverse event and concomitant medication collection

Re-baseline Visit	
Physical examination (within 1 month)Urine pregnancy test (females only)Body weightVital signsECG (within 1 month)Hematology and urinalysis (within 1 month)Biochemistry	
Anti-avalglucosidase alfa antibodies and neutralizing antibodies in ADA-positive patientsAnti-alglucosidase alfa IgG antibodies (only patients who were previously treated with alglucosidase alfa)avalglucosidase alfa plasma PK samples (within 6 months)	
MRI (within 6 months)Skeletal muscle needle or open biopsy (within 6 months)^cUrine Hex4 sample collection (within 1 month)Exploratory biomarker urine sample collection (within 1 month)Exploratory biomarker plasma sample collection (within 1 month)	
6MWT (within 1 month)PFT (within 1 month)microRNA plasma sample collection (within 1 month)Serum samples for skeletal muscle RNA expression analysis (within 6 months)^c
End of Study Visit	
Physical examinationUrine pregnancy test (females only)Body weightVital signsECGHematology and urinalysisBiochemistry	
Anti-avalglucosidase alfa antibodies and neutralizing antibodies in ADA-positive patientsAnti-alglucosidase alfa IgG antibodies (only patients who were previously treated with alglucosidase alfa)avalglucosidase alfa plasma PK samples	
MRISkeletal muscle needle or open biopsy (within 6 months)^cUrine Hex4 sample collectionExploratory biomarker urine sample collectionExploratory biomarker plasma sample collection	
6MWTPFTmicroRNA plasma sample collectionSerum samples for skeletal muscle RNA expression analysis (within 6 months)^cInfusion of avalglucosidase alfa

Follow-up Visit: Adverse event and concomitant medication collection

Additional Follow-up Phase: An additional follow-up phase will begin after the patient has completed the 6-year study period, and will last until avalglucosidase alfa is approved in the patient's country, except in the UK, Germany and Denmark, where the duration of the additional follow-up phase will be up to the approval in the country or limited to a maximum of 2 years, whichever occurs first (ie, for patients in the UK, Germany and Denmark, the total study duration per patient is 8 years at the maximum including the initial 6-year period and the additional 2-year follow-up).

a Note that medical/surgical history, and Pompe disease history, including GAA gene mutations will be imported from the patient's prior avalglucosidase alfa study file in the database when possible. ECG, hematology, biochemistry, and urinalysis data from first day of avalglucosidase alfa infusion (ie, prior to first infusion in any prior avalglucosidase alfa study) will be entered by the study site into the database.

b In case of temporary treatment discontinuation visit and assessment schedules will be adapted to the absence of infusion of avalglucosidase alfa (GZ402666) as outlined in [Section 10.1.3.8](#).

c Muscle biopsy is not required in patients in whom the prior muscle biopsy, obtained in a prior avalglucosidase alfa study, had a glycogen content <5% unless the patient shows significant clinical decline.

6MWT = 6-minute walk test; ADA = anti-drug antibody, ECG = electrocardiogram; Hex4 = glucose tetrasaccharide; IgG = immunoglobulin G; MRI = magnetic resonance imaging; PFT = pulmonary function testing; PK = pharmacokinetic(s)

1.2 STUDY FLOW CHART

1.2.1 Patients receiving same dose as received in a prior avalglucosidase alfa study (inclusive of 20 mg/kg qow)

Phase	Baseline ^a	Avalglucosidase alfa Treatment Phase					
Timing ^c		Biweekly	Monthly ^d	Quarterly	Every 6 months	At 6 months, yearly thereafter	Every 2 years ^b
Informed consent for extension	X						
Visit at clinical site	<	-	-	-	-	-	>
Inclusion/exclusion criteria	X						
Demographic	X						
Concomitant medications	<	-	-	-	-	-	>
Study treatment administration	within a ±7-day window ^e						
avalglucosidase alfa infusion		X					
Vital signs		X					
Safety^f	within a ±14-day window ^e						
Physical examination					X		
Urine pregnancy test ^g	X		X				
Body weight				X			
ECG	X				X		
Hematology, urinalysis ^h					X		
Biochemistry ^h			X For first 3 years since enrollment	X After first 3 years since enrollment			
Anti-avalglucosidase alfa antibodies and neutralizing antibodies in ADA-positive patients ⁱ			X For first 6 months	X After first 6 months			
Anti-alglucosidase alfa IgG antibodies (only patients who were previously treated with alglucosidase alfa)					X		
Adverse event collection	<	-	-	-	-	-	>

Phase	Baseline ^a	Avalglucosidase alfa Treatment Phase					
Timing ^c		Biweekly	Monthly ^d	Quarterly	Every 6 months	At 6 months, yearly thereafter	Every 2 years ^b
Pharmacokinetics	within a ±14-day window ^e						
avalglucosidase alfa plasma samples						X	
Pharmacodynamics ^f	within a ±14-day window ^e						
MRI ^j							X
Skeletal muscle biopsy ^k							X
Urine Hex4 samples ^h						X	
Exploratory biomarker plasma samples ^h						X	
Exploratory biomarker urine samples ^h						X	
Efficacy ^f	within a ±14-day window ^e						
6MWT					X		
PFT					X		
Pharmacogenetics ^f	within a ±14-day window ^e						
Plasma samples for circulating microRNA analyses ^h						X	
Serum samples for skeletal muscle RNA expression analyses ^k							X

a Medical/surgical history, and Pompe disease history, including GAA gene mutations, will be imported from the patient's prior avalglucosidase alfa study file in the database when possible. ECG, hematology, biochemistry, and urinalysis data from first day of avalglucosidase alfa infusion (ie, prior to first infusion in any prior avalglucosidase alfa study) will be entered by the study site into the database.

b If the patient discontinues from the study early, then they should undergo the EOS and 30-Day follow-up visits; please refer to [Section 1.2.3](#) for details of procedures to be performed during these visits.

c In case of temporary treatment discontinuation visit and assessment schedules will be adapted to the absence of infusion of avalglucosidase alfa (GZ402666) as outlined in protocol [Section 10.1.3.8](#).

d Monthly assessments start at study Week 4.

e Patients should adhere to original target infusion and visit schedule based on first infusion in LTS13769.

f See [Section 10.1](#) for specific details on the timing of each assessment relative to avalglucosidase alfa infusion during the treatment period.

g Females only.

h Fasted blood, urine, or plasma sample.

i Additional samples may be taken for circulating immune complex detection, IgE, serum tryptase, and complement activation, following moderate, severe, or recurrent mild IARs suggestive of hypersensitivity reactions (see [Section 8.8.2](#) for details).

j MRI obtained from the previous study will be used as baseline.

k Muscle biopsy is not required in patients in whom the prior muscle biopsy, obtained in a prior avalglucosidase alfa study, had a glycogen content <5% unless the patient shows significant clinical decline.

<-> = collection at every visit; 6MWT = 6-minute walk test; ADA = anti-drug antibody, ECG = electrocardiogram; EOS = end of study; ERT = enzyme replacement therapy; Hex4 = glucose tetrasaccharide; IgG = immunoglobulin G; IMP = investigational medicinal product; MRI = magnetic resonance imaging; PFT = pulmonary function testing.

1.2.2 Patients being switched to avalglucosidase alfa 20 mg/kg qow from previous different dose

Phase	Re-baseline ^a	Avalglucosidase alfa Treatment Phase					
Timing^c		Biweekly	Monthly ^d	Quarterly	Every 6 months	At 6 months, yearly thereafter	Every 2 years ^b
Informed consent for patients switching to 20 mg/kg qow	X						
Visit at clinical site	<	-	-	-	-	-	>
Concomitant medications	<	-	-	-	-	-	>
Study treatment administration	within a ±7-day window ^e						
Avalglucosidase alfa infusion	X	X					
Vital signs	X	X					
Safety^f	within a ±14-day window ^e						
Physical examination	X				X		
Urine pregnancy test ^g	X		X				
Body weight	X			X			
ECG	X				X		
Hematology, urinalysis ^h	X				X		
Biochemistry ^h	X		X For first 3 years since enrollment	X After first 3 years since enrollment			
Anti-avalglucosidase alfa antibodies and neutralizing antibodies in ADA-positive patients ⁱ	X		X For first 6 months	X After first 6 months			
Anti-alglucosidase alfa IgG antibodies (only patients who were previously treated with alglucosidase alfa)	X				X		
Adverse event collection	<	-	-	-	-	-	>
Pharmacokinetics	within a ±14-day window ^e						
Avalglucosidase alfa plasma samples	X					X	

Phase	Re-baseline ^a	Avalglucosidase alfa Treatment Phase					
Timing ^c		Biweekly	Monthly ^d	Quarterly	Every 6 months	At 6 months, yearly thereafter	Every 2 years ^b
Pharmacodynamics^f	within a ±14-day window ^e						
MRI	X						X
Skeletal muscle biopsy ^g	X						X
Urine Hex4 samples ^h	X					X	
Exploratory biomarker plasma samples ^h	X					X	
Exploratory biomarker urine samples ^h	X					X	
Efficacy^f	within a ±14-day window ^e						
6MWT	X				X		
PFT	X				X		
Pharmacogenetics^f	within a ±14-day window ^e						
Plasma samples for circulating microRNA analyses ^h	X					X	
Serum samples for skeletal muscle RNA expression analyses ^j	X						X

a The "Re-baseline" will only apply to patients who have switched from 5 or 10 to 20 mg/kg. Medical/surgical history, and Pompe disease history, including GAA gene mutations, will be imported from the patient's prior avalglucosidase alfa study file in the database when possible. ECG, hematology, biochemistry, and urinalysis data from first day of avalglucosidase alfa infusion (ie, prior to first infusion in any prior avalglucosidase alfa study) will be entered by the study site into the database.

b If the patient discontinues from the study early then they should undergo the EOS and 30-Day follow-up visits, please refer to [Section 1.2.3](#) for details of procedures to be performed during these visits.

c In case of temporary treatment discontinuation visit and assessment schedules will be adapted to the absence of infusion of avalglucosidase alfa as outlined in protocol [Section 10.1.3.8](#).

d Monthly assessments start at study Week 4.

e Patients should adhere to original target infusion and visit schedule based on first infusion of 20 mg/kg in the LTS13769 study.

f See [Section 10.1](#) for specific details on the timing of each assessment relative to avalglucosidase alfa infusion during the treatment period.

g Females only.

h Fasted blood, urine, or plasma sample.

i Additional samples may be taken for circulating immune complex detection, IgE, serum tryptase, and complement activation, following moderate, severe, or recurrent mild IARs suggestive of hypersensitivity reactions (see [Section 8.8.2](#) for details).

j Muscle biopsy is not required in patients in whom the prior muscle biopsy, obtained in a prior avalglucosidase alfa study, had a glycogen content <5% unless the patient shows significant clinical decline.

<-> =collection at every visit; 6MWT =6-minute walk test; ADA =anti-drug antibody, ECG =electrocardiogram; EOS =end of study; ERT =enzyme replacement therapy; Hex4 =glucose tetrasaccharide;

IgG =immunoglobulin G; IMP =investigational medicinal product; MRI =magnetic resonance imaging; PFT =pulmonary function testing; qow =every other week.

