10.1.2.5 At 6 months and yearly thereafter

The following assessments will be performed at 6 months and yearly thereafter:

- Avalglucosidase alfa PK plasma sample collection.
- Urine Hex4 sample collection.
- Exploratory biomarker urine sample collection.
- Exploratory biomarker plasma sample collection.
- Plasma sample collection for microRNA analyses.

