10.1.2.6 Every 2 years

The following assessments will be performed every 2 years:

- MRI.
- Skeletal muscle biopsy (not required in patients in whom the prior muscle biopsy, obtained in a prior avalglucosidase alfa study, had a glycogen content <5% unless the patient shows significant clinical decline).
- Serum sample collection for skeletal muscle RNA expression analyses (not required in patients in whom the prior muscle biopsy, obtained in a prior avalglucosidase alfa study, had a glycogen content <5% unless the patient shows significant clinical decline).

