11.7 PHARMACODYNAMIC AND EXPLORATORY BIOMARKER ANALYSIS

Pharmacodynamic endpoints as described in [Section 9.3](#) will be summarized using descriptive statistics at each scheduled study visit. Observed measurements, as well as change from baseline, will be summarized. If a linear trend in the change of a pharmacodynamic endpoint is observed, longitudinal model may be employed to model change from baseline over time. In addition, 95% confidence intervals (CI) of changes will be presented.

Evaluation of intact muscle and fatty replacement from MRI will be descriptive using a grading scale and, if feasible, quantitative using a numeric method of determining the degree (%) of overall fatty replacement of muscle from the skeletal muscle MRI and an individual (%) measure for the quadriceps. A correlative measure comparing the biopsied muscle and its MRI counterpart will also be performed.

Urine Hex4 levels will be summarized using descriptive statistics at each scheduled study visit. Observed measurements, as well as change from baseline, will be summarized. If a linear trend in the change of urine Hex4 levels is observed, a longitudinal model may be employed to model change from baseline over time. In addition, 95% CIs of changes will be presented. Due to the small number of patients, nonlinear relationship will not be formally characterized.

To explore the relationship between PK endpoints and urine Hex4 levels, scatter plots and linear mixed model may be used as appropriate.

To explore the relationship between glycogen content and biomarkers, correlational statistics (Spearman or Pearson) at each scheduled study visit will be used. In addition, scatter plots and linear regression analysis will be used to describe the relationship between glycogen content and each biomarker.

Similar analyses will be carried out to explore the relationship between other pharmacodynamic endpoints, exploratory biomarkers, and exploratory efficacy assessments.

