Week 11 in TDR (71)	Week 11	64 to 77 days
Week 13 in TDR (85)	Week 13	78 to 91 days
Week 15 in TDR (99)	Week 15	92 to 105 days
Week 17 in TDR (113)	Week 17	106 to 119 days
Week 19 in TDR (127)	Week 19	120 to 133 days
Week 21 in TDR (142)	Week 21	134 to 148 days
Week 23 in TDR (156)	Week 23	149 to 162 days
Week 25 in TDR (169)	Week 25	163 to 176 days/(1 st day of LTS – 1)**
Month 6 in LTS (365)	Week 52	(1 st day of LTS) to 548 days
Month 18 in LTS (730)	Week 104	549 to 913 days
Month 30 in LTS (1095)	Week 156	914 to 1278 days
Month 42 in LTS (1460)	Week 208	1279 to 1643 days
Month 54 in LTS (1825)	Week 260	1644 to 2008 days
Month 66 in LTS (2190)	Week 312	2009 to 2373 days
Month 72 in LTS (2372)	Week 338	2374 to 2402 days

*Study days are days since the first infusion in the TDR12857 study.

**For patients who enrolled in LTS13769, the upper boundary of the window is 176 days or (1st day of LTS – 1), whichever is earlier; for patients who didn't enroll in LTS13769, use study day 176 as cutoff.

Table 6 – Plasma concentration of avalglucosidase alfa

VISIT (target study day*)	Analysis Visit	Analysis Visit Window (in study days*)
Baseline	Baseline	
Week 1 in TDR (1)	Week 1	1 to 42 days
Week 13 in TDR (85)	Week 13	43 to 127 days
Week 25 in TDR (169)	Week 25	128 to 273 days/(1 st day of LTS – 1)**
Month 6 in LTS (365)	Week 52	(1 st day of LTS) to 548 days
Month 18 in LTS (730)	Week 104	549 to 913 days
Month 30 in LTS (1095)	Week 156	914 to 1278 days
Month 42 in LTS (1460)	Week 208	1279 to 1643 days
Month 54 in LTS (1825)	Week 260	1644 to 2008 days
Month 66 in LTS (2190)	Week 312	2009 to 2373 days
Month 72 in LTS (2372)	Week 338	2374 to 2402 days

*Study days are days since the first infusion in the TDR12857 study.

**For patients who enrolled in LTS13769, the upper boundary of the window is 273 days or (1st day of LTS – 1), whichever is earlier; for patients who didn't enroll in LTS13769, use study day 273 as cutoff.

Table 7 –MRI, muscle biopsy

VISIT (target study day*)	Analysis Visit	Analysis Visit Window (in study days*)
Baseline	Baseline	
Week 27 in TDR (184)	Week 27	92 to 273 days/(1 st day of LTS – 1)**
Month 24 in LTS (365)	Week 52	(1 st day of LTS) to 1278 days
Month 48 in LTS (1095)	Week 156	1279 to 2008 days
Month 72 in LTS (2372)	Week 338	2009 to 2402 days

*Study days are days since the first infusion in the TDR12857 study.

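### At Months 24 and 48 the nearest scheduled Hex4 or biomarker sample is about six months from the biopsy and MRI, and the SAP's visit labels would match them to Hex4 from 18 months earlier

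*Protocol*

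**What the plan says.** Protocol 1.2.1 and 1.2.2 list urine Hex4 and the exploratory plasma and urine biomarkers in the column "At 6 months, yearly thereafter". Section 10.1.2.5 repeats it: "The following assessments will be performed at 6 months and yearly thereafter". Biopsy and MRI are in the two-yearly column, and 10.1.2.6 says "The following assessments will be performed every 2 years". Pharmacodynamic assessments are to be done "within a ±14-day window". The protocol gives no month numbers.

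Protocol 11.7 then states: "To explore the relationship between glycogen content and biomarkers, correlational statistics (Spearman or Pearson) at each scheduled study visit will be used". It adds that similar analyses will relate the other pharmacodynamic endpoints, biomarkers and efficacy measures.

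SAP Appendix B supplies the months. Table 5 (Hex4) has Months 6, 18, 30, 42, 54 and 66, and a last row that begins "Month 72 in LTS (2372", with the window "2374 to 2402 days". Table 7 (MRI and biopsy) has Months 24, 48 and 72. There is no window table for the plasma and urine biomarkers.

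**The concern.** A correlation at a visit needs both measurements at that visit. At Months 24 and 48 the plan schedules the biopsy and MRI but not the Hex4, plasma or urine samples, so an analyst following Protocol 11.7 has nothing to correlate there.

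The larger risk is a silent one. The natural way to program a by-visit correlation is to join the two datasets on the analysis visit. With the labels now printed, that join succeeds but matches samples taken at very different times. The output would look complete, and a marker that does follow muscle glycogen could appear unrelated to it. Protocol 4.2.2.2 offers Hex4 as a possible means of monitoring efficacy, so this relationship is of real interest.

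**Working it through.** **Plan's own targets.** LTS Month m should fall at study day (m + 6) × 365.25 / 12, since LTS starts about six months after the first parent-study infusion.

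| LTS month | Computed day | SAP Table 1 | SAP Table 7 |
|---|---|---|---|
| 24 | 913.1 | 912 (Week 130) | 365 (Week 52) |
| 48 | 1643.6 | 1642 (Week 234) | 1095 (Week 156) |
| 72 | 2374.1 | 2372 (Week 338) | 2372 (Week 338) |

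Table 1 is reproduced to within about 2 days. Table 7 is not: 912 − 365 = 547 and 1642 − 1095 = 547 days too early.

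Table 7's windows do fit the correct targets. The midpoint of 912 and 1642 is 1277, and that of 1642 and 2372 is 2007; the windows break at 1278/1279 and 2008/2009. Only the target days and labels are wrong.

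**Shared visits.** Reading the Hex4 rule as 6 + 12k gives Months 6, 18, 30, 42, 54 and 66. That is six of the seven LTS rows in Table 5; the rule does not produce Month 72.

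- Month 24 (day 912): bracketing Hex4 on days 730 and 1095, gaps 182 and 183 days.
- Month 48 (day 1642): bracketing Hex4 on days 1460 and 1825, gaps 182 and 183 days.
- Month 72 (day 2372): Hex4 listed on the same target day, in the SAP only.

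A 14-day tolerance cannot bridge 182 days.

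**Matching on labels, Months 24 and 48.** A biopsy on day 912 lies in Table 7's Week 52 window (first LTS day to 1278). Hex4 Week 52 is targeted at day 365, so the gap is 547 days. A biopsy on day 1642 lies in Week 156 (1279 to 2008). Hex4 Week 156 is targeted at day 1095, again 547 days earlier. Both gaps are about 18 months. Correcting the labels to Weeks 130 and 234 removes the false match but creates no pair, because Table 5 has neither label.

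**Matching on labels, Month 72.** Day 2372 falls in Table 5's Week 312 window (2009 to 2373), not in Week 338 (2374 to 2402). The biopsy that day is labelled Week 338. Of the 29 days in 2372 ± 14, 16 (2358 to 2373) go to Week 312. Appendix B keeps the value closest to target, so an on-target Month 66 sample (day 2190) would displace the Month 72 one.

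**Attenuation (assumption).** Suppose a patient's marker follows an AR(1) process with six-month correlation φ between 0.6 and 0.9. The documents give no value. The true correlation is then multiplied by:

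- one sample 6 months away, φ: 0.60 to 0.90;
- mean of the two bracketing samples, φ / √((1 + φ²)/2): 0.73 to 0.95;
- one sample 18 months away, φ³: 0.22 to 0.73.

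**Where pairs exist.**

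- Parent study: both at baseline, then Hex4 at Week 25 (day 169) and biopsy/MRI at Week 27 (day 184), 15 days apart.
- Re-baseline: both, but for dose switchers only, and the biopsy may be up to 6 months old.
- End of Study: both, with the same 6-month allowance for the biopsy.

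**The case against.** A reader might infer that no pairs arise at any regular treatment-phase visit. The documents do not support that: SAP Table 5 lists Hex4 at Month 72, which is also a biopsy visit. The parent-study pairs count too, since SAP section 2 analyses both studies together. The protocol wording alone would even allow Month 6 followed by anniversaries (12, 24, 36 and so on), which would pair all three biopsy visits. SAP Tables 5 and 6 do not read it that way.

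A reader might also fault the SAP for running this correlation badly. In fact SAP 2.4.7 does not carry it. That section keeps biopsy versus MRI and PK versus Hex4, the latter limited to visits where both are measured, and SAP 2.1.6 defers the exploratory biomarkers to separate reporting. This stands. But Protocol section 11 says changes to the analysis will be set out in the SAP, and SAP 1.6 does not list this one as dropped. Hex4 also remains a secondary endpoint in the erratum.

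Nor is replacing biopsies a stated aim. No document prescribes a join on visit labels; it is simply what by-visit analysis invites. The AR(1) range is an assumption, and a stable between-patient component would soften the attenuation. Biopsies are also conditional: patients with prior glycogen below 5% need none unless they decline clinically, so pairs are fewer in any case.

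**Conclusion.** The concern holds for Months 24 and 48: two of the three two-yearly biopsy/MRI visits have no Hex4 or plasma/urine biomarker sample nearer than about six months. For the plasma and urine biomarkers this assumes they follow the Hex4 months, since they share its flow-chart column. At Month 72 a pair exists for Hex4 only, through the SAP only, and Table 5's window then separates the two labels. As printed, label matching would pair Months 24 and 48 with Hex4 from 547 days earlier. That gap comes directly from the SAP tables; the attenuation factors rest on the assumed φ.

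The mismatch reaches MRI versus Hex4 or biomarkers as well. It does not touch biopsy versus MRI or the serum sample for muscle RNA, which share the biopsy column, or comparisons with 6MWT and PFT, which are six-monthly and meet both series. The analysis is exploratory, so this is a repair that should be made and not a threat to the primary safety conclusions.

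**What to change.** 1. **Pair by actual date.** In Protocol 11.7, and in the SAP or the separate biomarker plan if the analysis is kept, replace the visit-by-visit wording. Use a sample within a stated maximum number of days. Alternatively, for Months 24 and 48, interpolate on the log scale between the bracketing samples (18 and 30; 42 and 54). Use the Month 72 or End of Study sample for the last biopsy. Do not reach forward to a distant later sample: in the additional follow-up phase Hex4 is taken only at End of Study, possibly years on. Rule out joins on visit labels. If the analysis is dropped, say so.
2. **Correct Appendix B.** In Table 7, set Month 24 to day 912, Week 130, and Month 48 to day 1642, Week 234. In Table 5, start the Week 338 window before day 2372 (for example at 2282, as in Table 1) and end Week 312 the day before. State which months the yearly schedule means.
3. **Sample at remaining biopsy/MRI visits.** Collect the fasted urine and plasma at the same visit.

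Items 1 and 2 cost wording and a little programming. Item 3 costs one urine and one plasma sample at a visit already attended. The drawback of interpolation is that its values are smoother than same-day values and need both bracketing samples.
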